**Medications:**

26. Currently using and plan to use the following medications during the study
  - Rivaroxaban or drugs in the same class
  - Dual anti-platelets therapy
  - Other anticoagulants ([Table 5](#))
  - Combined P-gp and CYP3A inhibitors and inducers ([Table 5](#)).

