#### Type of Participant

2. Participants must be at high-risk for COVID-19 progression by fulfilling at least **one** of the following criteria at screening:

- Age  $\geq 65$  years
- Presence of chronic pulmonary disease, chronic obstructive pulmonary disease (COPD), pulmonary hypertension
- Diabetes mellitus (type 1 or type 2), requiring oral medication or insulin for treatment
- Hypertension, requiring at least one oral medication for treatment
- Immunocompromised status due to disease (e.g., those living with human immunodeficiency virus with a CD4 T-cell count of  $<200/\text{mm}^3$ )
- Immunocompromised status due to medication (e.g., taking 20 mg or more of prednisone equivalents a day, anti-inflammatory monoclonal antibody therapies, cancer therapies)
- Any chronic disease that is associated with high risk for severe COVID disease in the opinion of the site investigator
- Body mass index  $\geq 35 \text{ kg/m}^2$  (based on self-reported weight and height).

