## **6.10. Concomitant Therapy**

The prohibited medications in this study are other anticoagulants, and combined P-gp and CYP3A inhibitors and inducers because of their significant PK and PD interactions with rivaroxaban. Should administration of any prohibited drug ([Table 5](#)) be indicated for participants' clinical care, the study medication must be discontinued. Other drugs may have PK and PD interactions with rivaroxaban and thus are considered precautionary medications.

Refer to [Section 6.10.1](#) for prohibited medications and to [Section 6.10.2](#) for precautionary medications.

Whether the study medication should be discontinued or allowed to be used with these precautionary medications will be under the clinical judgement of the treating physician (i.e., either the PI, or the physician responsible for the patient's care if the participant is hospitalized).

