#### **6.10.1. Prohibited Medications**

**Table 5: Rivaroxaban prohibited medications/foods/supplements**

Drug Class	Examples (based on human in vivo data)	Known or Probable Effect
Anticoagulants	warfarin sodium (Coumadin®, Jantoven®), any medicine that contains heparin, including low molecular weight heparins, apixaban, Pradaxa [dabigatran], Savaysa [edoxaban], Bevyxxa [betrixaban], non-study Xarelto [rivaroxaban]	Increased risk of bleeding
Combined P-gp inhibitors and strong CYP3A4 inhibitors	cobicistat, conivaptan, indinavir, itraconazole, ketoconazole, posaconazole, ritonavir, saquinavir, telaprevir, telithromycin	Significant increase in rivaroxaban concentration
Combined P-gp inhibitors and moderate CYP3A4 inhibitors OR strong CYP3A4 inhibitors alone	amiodarone, azithromycin, clarithromycin, cyclosporine, diltiazem, dronedarone, erythromycin, fluconazole, grapefruit, lapatinib, mifepristone, nefazodone, nicardipine, ranolazine, tamoxifen, ticagrelor, verapamil, voriconazole	Moderate increase in rivaroxaban concentration in patients with normal renal function. Significant increase in rivaroxaban concentrations in patients with renal impairment
Combined P-gp inducers and strong CYP3A4 inducers	carbamazepine, dexamethasone, rifampin, St John's wort	Significant reduction in rivaroxaban concentration

Drug Class	Examples (based on human in vivo data  )	Known or Probable Effect
Inducers of P-gp	tipranavir	Effect may persist for several weeks following discontinuation of strong inducers of P-gp and/or CYP3A4 Significant reduction in rivaroxaban concentration Effect may persist for several weeks following discontinuation of strong inducers of P-gp and/or CYP3A4
Strong inducers of CYP3A4	bosentan, efavirenz, etravirine, fosphenytoin, naftillin, nevirapine, phenobarbital, phenytoin, primidone, rifabutin, rifapentine	Significant reduction in rivaroxaban concentration Effect may persist for several weeks following discontinuation of strong inducers of P-gp and/or CYP3A4

Modified from [UW 2020]

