## **7. Discontinuation/Withdrawal Criteria and Study Completion**

### **7.1. Discontinuation of Study Intervention**

Study intervention will be discontinued for the following reasons:

- Hospitalization, if the in-patient provider decides continuation of study treatment is contraindicated.
- Requirement for prohibited concomitant medications or other contraindication to study product
- Occurrence of an AE requiring discontinuation of study intervention (i.e., severe hypersensitivity, major bleeding or clinically relevant non-major bleeding)
- Request by participant to terminate study intervention
- Clinical reasons believed to be life-threatening by the physician, even if not addressed in this protocol
- Pregnancy.

Participants who stop study intervention should continue study participation while off of the study intervention, with continued evaluations as per the SoA. The reason for study intervention discontinuation should be recorded.

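### Entry criterion 26 names only combined P-gp/CYP3A drugs, but Table 5 also prohibits single-pathway drugs, so a person can be randomized whose study drug must then stop; recent inducer use is not addressed

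*Protocol*

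**What the plan says.** Four places in the protocol and one in the SAP bear on this.

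- **Protocol 5.5.2, criterion 26 (entry).** The lead-in is "Currently using and plan to use the following medications during the study". The only class listed for drug interaction is "Combined P-gp and CYP3A inhibitors and inducers", with a pointer to Table 5. The criterion also bars same-class drugs, dual antiplatelet therapy and other anticoagulants.
- **Protocol 6.10 (on study).** It opens: "The prohibited medications in this study are other anticoagulants, and combined P-gp and CYP3A inhibitors and inducers". It then says that if any prohibited drug, citing Table 5, is indicated for a participant's care, "the study medication must be discontinued".
- **Protocol 6.10.1, Table 5.** Besides anticoagulants and the combined classes, it covers strong CYP3A4 inhibitors alone (sharing a row with combined P-gp and moderate CYP3A4 inhibitors), P-gp inducers (tipranavir) and strong CYP3A4 inducers: "bosentan, efavirenz, etravirine, fosphenytoin, naftillin, nevirapine, phenobarbital, phenytoin, primidone, rifabutin, rifapentine". Against inducers it notes: "Effect may persist for several weeks following discontinuation of strong inducers of P-gp and/or CYP3A4".
- **Protocol 7.1.** Reasons to stop study intervention include: "Requirement for prohibited concomitant medications or other contraindication to study product".
- **SAP 11.1.2.** Participants who use prohibited medication before treatment discontinuation and Day 28 are excluded from the per-protocol (PP) analysis. No list is named.

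The primary analysis is in the ITT population (Protocol 10.5.1, SAP 11.1.1).

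**The concern.** The class that bars entry is narrower than the list that stops treatment. A site following criterion 26 as worded can randomize a person whose study drug must stop under 6.10 and 7.1. Protocol 3.2.3.1 says people at increased risk of drug interactions with rivaroxaban will be excluded, and the criterion does not fully deliver that.

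The second gap is in time. Table 5 describes an inducer effect that may outlast the inducer by weeks, yet no criterion looks back at recent use. Criteria 20 and 21, by contrast, set windows of 2 weeks for neuraxial procedures and 4 weeks for surgery.

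At stake are dilution of the ITT comparison by participants with little or reduced exposure, avoidable discontinuations, and an undefined term in the PP exclusion. The case is foreseeable: inclusion criterion 2 gives "those living with human immunodeficiency virus with a CD4 T-cell count of" a stated threshold as an example of high risk, and efavirenz, etravirine and nevirapine, in the single-pathway inducer row, are HIV drugs (general knowledge, not stated in the protocol).

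**Working it through.** **1. The lists side by side**

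| Class in Table 5 | Named in criterion 26 and the opening of 6.10? | Study drug stops (6.10 via Table 5; 7.1)? |
|---|---|---|
| Other anticoagulants | Yes | Yes |
| Combined P-gp and CYP3A4 inhibitors | Yes | Yes |
| Strong CYP3A4 inhibitors alone | No | Yes |
| Combined P-gp and CYP3A4 inducers | Yes | Yes |
| P-gp inducers | No | Yes |
| Strong CYP3A4 inducers | No | Yes |

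Three classes pass entry as worded and trigger a stop. Phenytoin and efavirenz fall in the last.

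**2. Timing in criterion 26**

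- *Literal reading of the lead-in:* use must be both current and planned. A current user who intends to stop, or a non-user who intends to start, is not literally excluded.
- *Recent past user:* neither a current nor a planned user. This person passes whether the two conditions are joined by and or by or. The cause is the missing look-back, not the conjunction.

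**3. The plan's own sample size**

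Inputs (Protocol 10.1, SAP 9.1.1): control 30%, rivaroxaban 19.5%, one-sided 2.5%, power 80%, drop-out 10%.

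n = [z₁₋α √(2p̄(1−p̄)) + z₁₋β √(p₁(1−p₁) + p₂(1−p₂))]² / (p₁−p₂)², with p̄ = 0.2475:

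- 1.960 × √0.3725 = 1.196
- 0.8416 × √0.3670 = 0.510
- (1.196 + 0.510)² / 0.105² = 2.911 / 0.011025 = 264 per group
- 264 / 0.9 = 293.3, rounded up to 294, as stated

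**4. Dilution, as an illustration only**

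The documents give no share of affected participants. Assume a share f of the rivaroxaban arm gets no benefit and progresses at 30%. Then p₂ = 0.195(1−f) + 0.30f, and the difference is 10.5(1−f) points. Power at 264 per group, from the same formula:

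| f (assumed) | p₂ | Difference (points) | Power |
|---|---|---|---|
| 0 | 19.50% | 10.50 | 80.0% |
| 2% | 19.71% | 10.29 | 78.3% |
| 5% | 20.03% | 9.98 | 75.5% |
| 10% | 20.55% | 9.45 | 70.6% |

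With 300 in the arm, 2%, 5% and 10% are 6, 15 and 30 people. For a given share, no benefit at all is the pessimistic case, since Table 5 speaks of a significant reduction in concentration, not of none.

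**5. Consequence for the PP set**

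A participant whose study drug is stopped at once may leave the PP set anyway, because SAP 7.1 requires the intervention to be received as planned. The choice of list therefore matters mainly for Table 5 users who kept taking study drug. Someone who stopped an inducer before Day 1 is not reached by the SAP 11.1.2 rule under either list.

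**The case against.** The best reply is that Table 5 already governs. Criterion 26 cites it, the stop rule in 6.10 is tied to it, and 6.10 sends the reader to 6.10.1 for the prohibited list. With the intent stated in 3.2.3.1, a site could reasonably apply the whole table at entry. That is a fair reading, but not the only one: the citation follows a phrase that names the combined class, 6.10 repeats that phrase, and Table 5 gives other classes entries of their own. Two careful sites could differ. For the PP rule the reply is stronger. Table 5 is the natural meaning of prohibited, so a reader who infers that PP membership is genuinely open would go too far; SAP 11.1.2 needs a line of clarification.

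A reader might also infer a raised bleeding risk from drugs that pass criterion 26. The documents do not show it. The row containing strong CYP3A4 inhibitors alone gives a moderate increase in normal renal function and a significant one only in renal impairment. Criterion 16 removes known stage IV or dialysis kidney disease. The row does not say which examples are strong CYP3A4 inhibitors alone, so no named drug can be tied to that group.

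The HIV route is narrower than it may look. HIV with a low CD4 count is one example under immunocompromised status, and ritonavir, cobicistat, indinavir and saquinavir are in a combined row that criterion 26 already covers.

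Finally, SAP 13.2 already summarizes prior and concomitant medications by arm and preferred name, so a recently stopped inducer would appear there. This stands, with limits: those tables cover the Safety population, do not group drugs by Table 5 class, and give no participant-level flag.

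**Conclusion.** The inconsistency is real and lies mainly between the entry wording and Table 5. Following the text can put a person into the trial whose study drug must stop straight away and who remains in ITT. The missing look-back is a separate omission: Table 5 says only that the effect may persist, and whether recent use should bar entry is a clinical decision.

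The number affected is unknown. The effect on the primary comparison is probably small, on the assumption that the share is a few percent at most: about 2 points of power at 2% and 4 to 5 at 5%, even with no benefit in those participants. A share near 10% would cost about 9 points, but nothing in the documents suggests one. These figures describe the design as planned. The trial crossed its futility boundary and randomization ceased as of 4 February 2021 (SAP Section 4), and nothing here shows that this gap contributed to that result.

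**What to change.** **Protocol.** Reconcile criterion 26, the opening of 6.10, Table 5 and 7.1 so that one list and one time frame govern entry and discontinuation. Settle whether the two conditions in the lead-in to criterion 26 are both required, and address recent past use in light of Table 5's persistence note. Which drugs and what interval apply is for the sponsor's clinical team. This helps only a restart or a later protocol that reuses the text.

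**SAP.** This part can still affect the analysis, since it follows database lock.

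- In 11.1.2, state that Table 5 is the list defining the PP exclusion. This is an analysis definition and does not settle the clinical rule.
- Derive a flag for use of any Table 5 class at or before Day 1 from the medication data already collected at screening and Day 1 (Protocol 8.1 and 9.1). Tabulate it by arm for the ITT population, alongside the 13.2 summaries.

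**Cost.** A few sentences and one derived variable, with no new data. The PP set may shrink slightly, and eligibility would narrow slightly if entry were aligned to Table 5.

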## **6. Study Intervention- Rivaroxaban or Placebo**

Participants will be randomly assigned to either the rivaroxaban group or placebo, in parallel to receive:

- Rivaroxaban group: 10mg (1 tablet) taken orally each day for 21 days.
- Placebo group: 1 tablet taken orally each day for 21 days.

The rivaroxaban (10mg) used in the active group will be Xarelto® 10mg tablet commercially marketed in the US.

For the placebo group, a placebo-equivalent will be used. This will be an over the counter dietary multi-vitamin supplement tablet, commercially marketed with their Product # 501-01 in the US by Geri-Care Pharmaceuticals Corp, based on its suitability to maintain masking to the extent possible.

The active and placebo tablets will not be identical in appearance; but will be similar in size, shape and color. Moreover, the bottles will be identical.

The bottle of medication the participants receive will not identify the treatment allocation. The active or placebo bottles will be labeled for investigational use with a randomized number to maintain blinding.

Refer to [Section 6.8](#) for preparation, handling, storage and accountability of the study IPs.

## **6.1. Rationale for Study Intervention Selection**

Refer to [Section 3.2.2](#) for the rationale for use of rivaroxaban for treatment of mild COVID-19 and to [Section 3.2.3.1](#) for benefits and risks of rivaroxaban.

## **6.2. Management of Participants to Limit Risks of SARS-CoV-2 Transmission**

To limit the transmission of SARS-CoV-2, remote monitoring will be done as much as it is feasible via video conference, text message, telephone or other methods, as appropriate. In-person or home visits may be required for administration or monitoring.

For any in-person contact, local guidance for COVID-19-related safety measures will be followed.

## **6.3. Guidance on COVID-19 to Ensure Participant and Healthcare Worker Safety**

COVID-19 specific guidance from public health authorities in the country in which the study will be conducted should be followed.

As an example, the FDA Guidance for Industry on COVID-19 provides general considerations to assist the Sponsor in assuring the safety of trial participants, maintaining compliance with good clinical practice (GCP), and minimizing risks to trial integrity for the duration of the COVID-19 public health emergency [[FDA 2020](#)]. For example, the Sponsor should consider each circumstance, focusing on the potential impact on the safety of trial participants, and modify study conduct accordingly. Sponsors, in consultation with clinical principal investigators (PIs) and Institutional Review Boards (IRBs)/Independent Ethics Committees (IECs), may determine that the protection of a participant's safety, welfare, and rights is best served by continuing a study participant in the trial as per the protocol or by discontinuing the administration or use of the investigational product or even participation in the trial. Such decisions will depend on specific circumstances, including the nature of the investigational product, the ability to conduct appropriate safety monitoring, etc.

Changes in study visit schedules, missed visits, or patient discontinuations may lead to missing information (e.g., for protocol-specified procedures). It will be important to capture specific information in the case report form that explains the basis of the missing data, including the relationship to COVID-19 for missing protocol-specified information (e.g., from missed study visits or study discontinuations due to COVID-19).

For instances where efficacy endpoints are not collected, the reasons for failing to obtain the efficacy assessment should be documented (e.g., identifying the specific limitation imposed by COVID-19 leading to the inability to perform the protocol-specified assessment).

## **6.4. Dose Modification and Toxicity Management**

There will be no dose modification.

Participants who experience major bleeding or clinically relevant non-major bleeding will have the study intervention discontinued (see [Section 7.1](#)) and managed according to standard of care.

Participants who experience other AEs due to the study medication may discontinue the study medication per the clinical judgment of the investigator.

At each visit, the participant will be asked if any bleeding events have occurred. Major bleeding events will be recorded as AESIs and non-major bleeding events will be recorded as AEs, in the eCRF. The following definitions will apply.

#### **6.4.1. Definitions of Bleeding Severity**

The following definitions are based on the guidance for non-surgical patients by the International Society on Thrombosis and Hemostasis (ISTH)/Scientific and Standardization Committee (SCC).

##### **6.4.1.1. Definition of Major Bleeding**

- Fatal bleeding AND/OR
- Symptomatic bleeding in a critical area or organ, such as intracranial, intraspinal, intraocular, retroperitoneal, intra-articular or pericardial, or intramuscular with compartment syndrome. AND/OR
- Bleeding causing a fall in hemoglobin level of 2 g/dL (1.24 mmol/L) or more or leading to transfusion of two or more units of whole blood or red cells.

##### **6.4.1.2. Definition of Clinically Relevant Non-Major Bleeding**

A clinically relevant non-major bleed is an acute or subacute clinically overt bleed that does not meet the criteria for a major bleed but prompts a clinical response, in that it leads to at least one of the following:

- A hospital admission for bleeding, OR
- A physician guided medical or surgical treatment for bleeding, OR
- A change in antithrombotic therapy (including interruption or discontinuation of study drug).

In addition, bleeding events that lead to participant's discomfort, and impairment of activities of daily life are considered clinically relevant non-major bleeding.

Examples of clinically relevant non-major bleeding are:

- Epistaxis if it lasts for more than 5 minutes, if it is repetitive (i.e., 2 or more episodes of true bleeding, i.e., not just spots on a tissue, within 24 hours), or leads to an intervention (packing, electrocoagulation, etc)
- Gingival bleeding if it occurs spontaneously (i.e., unrelated to tooth brushing or eating), or if it lasts for more than 5 minutes
- Hematuria if it is macroscopic, and either spontaneous or lasts for more than 24 hours after instrumentation (e.g., catheter placement or surgery) of the urogenital tract

- Macroscopic gastrointestinal hemorrhage: at least 1 episode of melena/hematemesis, if clinically apparent
- Rectal blood loss, if more than a few spots
- Hemoptysis, if more than a few speckles in the sputum
- Intramuscular hematoma
- Large subcutaneous hematoma (more than 25 cm^2)
- Multiple source bleeding.

#### **6.4.1.3. Definition of Minimal Bleeding**

Other bleeding events that do not meet the criteria for either major bleeding or clinically relevant non-major bleeding are considered minimal bleeding.

### **6.5. Safety Monitoring**

Safety monitoring will take place once the informed consent has been signed. On Day 1, prior to IP, the participant will be asked about his or her health and about any bleeding issues prior to taking the first dose. The participant will then be in frequent contact with the study staff, with the final visit being 14 days after the last medication dose.

The participant will have a contact number to call the staff at any time should he or she have a non-emergency study related health issue that they need to discuss in between visits. As previously mentioned, if needed, additional contact with the study clinician or staff will be conducted at the request of the participant (e.g., if developing concerning symptoms or an AE). Refer to [Section 8](#) for more information.

If it is a health emergency, they will be asked to call the country nationwide health emergency number (like 911 in the USA). Refer to [Section 8](#) for more information regarding study procedures for safety.

### **6.6. Study Pausing Guidelines**

Pausing guidelines are put in place to address medical events necessitating a pause in enrollment and in participant dosing, and trigger IDMC reviews. Therefore, these guidelines are in effect during the active enrollment and dosing period. Any of the below conditions, if identified either by the study staff, investigator, the Sponsor or the IDMC, will trigger a pause of the enrollment and pause of administration of study intervention until the IDMC has reviewed the safety data and made a recommendation on how to proceed:

1. One report of anaphylaxis with or without bronchospasm within 4 hours of taking study intervention indicative of an immediate hypersensitivity reaction to the study intervention
2. One report of major bleeding judged as related to study intervention by the investigator.

## **6.7. Masking**

Every effort will be made to mask the assigned treatment groups. The participants will not be told of the assigned treatment groups and will not be informed that active and control treatment do not look identical. However, the participant could possibly find out this information because of features like embossment on the rivaroxaban tablets, which are not present on the placebo-equivalent tablets.

The study staff evaluating the participants will not be given the assigned treatment groups but could possibly find out if the participant's tablets become visible to them. Such occurrences will be documented. It is recognized that they could potentially bias the outcome assessments by the participant and study staff particularly for subjective measurements.

In order to preserve masking, household members of an enrolled participant will be excluded from participating in this study.

